#### 5.2.1 **Dose Selection/Modification**

#### 5.2.1.1 **Dose Selection**

The rationale for selection of doses to be used in this trial is provided in Section 4.0 - Background and Rationale.

Details on preparation and administration of pembrolizumab (MK-3475) are provided in the Pharmacy Manual.

#### 5.2.1.2 **Dose Modification**

The investigator may attribute each toxicity event to the study drug (pembrolizumab), cisplatin, or radiation alone, if appropriate. If a dose reduction for toxicity occurs, the dose of that agent may not be re-escalated. Dose modifications for additional rounds of treatment are based on the most recent dose utilized previously. Dose modifications for pembrolizumab (section 5.2.1.2.1), cisplatin (5.2.1.2.2) and radiation (5.2.1.2.3) are outlined below.

## **5.2.1.2.1** Dose Modification for Pembrolizumab

Adverse events (both non-serious and serious) associated with pembrolizumab exposure may represent an immunologic etiology. These adverse events may occur shortly after the first dose or several months after the last dose of treatment. Pembrolizumab must be withheld for drug-related toxicities and severe or life-threatening AEs as per Table 3 below. See Section 5.6.1 and Events of Clinical Interest Guidance Document for supportive care guidelines, including use of corticosteroids.

 Table 3 Dose Modification Guidelines for Pembrolizumab-Related Adverse Events

Toxicity	Hold Treatment For Grade	Timing for Restarting Treatment	Discontinue Subject
Diarrhea/Colitis	2-3	Toxicity resolves to Grade 0-1.	Toxicity does not resolve within 12 weeks of last dose or inability to reduce corticosteroid to 10 mg or less of prednisone or equivalent per day within 12 weeks.
	4	Permanently discontinue	Permanently discontinue
AST, ALT, or	2	Toxicity resolves to Grade 0-1	Toxicity does not resolve within 12 weeks of last dose.
Increased Bilirubin	3-4	Permanently discontinue (see exception below) 	Permanently discontinue
Type 1 diabetes mellitus (if new onset) or Hyperglycemia	T1DM or 3-4	Hold pembrolizumab for new onset Type 1 diabetes mellitus or Grade 3-4 hyperglycemia associated with evidence of beta cell failure.	Resume pembrolizumab when patients are clinically and metabolically stable.
Hypophysitis	2-3	Toxicity resolves to Grade 0-1	Toxicity does not resolve within 12 weeks of last dose or inability to reduce corticosteroid to 10 mg or less of prednisone or equivalent per day within 12 weeks.
	4	Permanently discontinue	Permanently discontinue
Hyperthyroidism	3	Toxicity resolves to Grade 0-1	Toxicity does not resolve within 12 weeks of last dose or inability to reduce corticosteroid to 10 mg or less of prednisone or equivalent per day within 12 weeks.
	4	Permanently discontinue	Permanently discontinue
Hypothyroidism	2-4	Therapy with pembrolizumab can be continued while treatment for the thyroid disorder is instituted	Therapy with pembrolizumab can be continued while treatment for the thyroid disorder is instituted.
Infusion Reaction	3-4	Permanently discontinue	Permanently discontinue
Pneumonitis	2	Toxicity resolves to Grade 0-1	Toxicity does not resolve within 12 weeks of last dose or inability to reduce corticosteroid to 10 mg or less of prednisone or equivalent per day within 12 weeks.
	3-4	Permanently discontinue	Permanently discontinue
Renal Failure or Nephritis	2	Toxicity resolves to Grade 0-1	Toxicity does not resolve within 12 weeks of last dose or inability to reduce corticosteroid to 10 mg or less of prednisone or equivalent per day within 12 weeks.
	3-4	Permanently discontinue	Permanently discontinue
All Other Drug- Related Toxicity 	3 or Severe	Toxicity resolves to Grade 0-1	Toxicity does not resolve within 12 weeks of last dose or inability to reduce corticosteroid to 10 mg or less of prednisone or equivalent per day within 12 weeks.
	4	Permanently discontinue	Permanently discontinue

Note: Permanently discontinue for any severe or Grade 3 drug-related AE that recurs or any life-threatening event.

 For patients with liver metastasis who begin treatment with Grade 2 AST or ALT, if AST or ALT increases by greater than or equal to 50% relative to baseline and lasts for at least 1 week then patients should be discontinued.

 Patients with intolerable or persistent Grade 2 drug-related AE may hold study medication at physician discretion. Permanently discontinue study drug for persistent Grade 2 adverse reactions for which treatment with study drug has been held, that do not recover to Grade 0-1 within 12 weeks of the last dose.

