#### 5.9 Subject Withdrawal/Discontinuation Criteria

Subjects may withdraw consent at any time for any reason or be withdrawn from the trial at the discretion of the investigator should any untoward effect occur. In addition, a subject may be withdrawn by the investigator or principal investigator if enrollment into the trial is inappropriate, the trial plan is violated, or for administrative and/or other safety reasons. Specific details regarding discontinuation or withdrawal are provided in Section 7.1.4 – Other Procedures.

A subject must be discontinued from the trial for any of the following reasons:

- The subject or legal representative (such as a parent or legal guardian) withdraws consent.
- Confirmed radiographic disease progression
- Unacceptable adverse experiences as described in Section 5.2.1.2
- Intercurrent illness that prevents further administration of treatment

- Investigator's decision to withdraw the subject
- The subject has a confirmed positive serum pregnancy test
- Noncompliance with trial treatment or procedure requirements
- The subject is lost to follow-up
- Administrative reasons

The End of Treatment and Follow-up visit procedures are listed in Section 6 (Protocol Flow Chart) and Section 7.1.5 (Visit Requirements). For those subjects discontinue treatment early, each subject will be followed for 30 days for adverse event monitoring (serious adverse events will be collected for 90 days after the end of treatment as described in Section 7.2.3.1). Subjects who discontinue for reasons other than progressive disease will have post-treatment follow-up for disease status until disease progression, initiating a non-study cancer treatment, withdrawing consent or becoming lost to follow-up. After documented disease progression each subject will be followed for overall survival until death, withdrawal of consent, or the end of the study, whichever occurs first.

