## 7.2.4.1 Table 6 Evaluating Adverse Events

An investigator, who is a qualified physician, will evaluate all adverse events as to:

V4.0 CTCAE Grading	Grade 1	Mild; asymptomatic or mid symptoms; clinical or diagnostic observations only; intervention not indicated.							
Grading	Grade 2	Moderate; minimal, local or noninvasive intervention indicated; limiting age-appropriate instrumental ADL.							
	Grade 3	Severe or medically significant but not immediately life-threatening; hospitalization or prolongation or hospitalization indicated;							
		disabling; limiting self-care ADL.							
	Grade 4	Life threatening consequences; urgent intervention indicated.							
	Grade 5	Death related to AE							
Seriousness	A serious adverse event is any adverse event occurring at any dose or during any use of Merck product that:								
	†Results in death ;	or							
	†Is life threatenin	g; or places the subject, in the view of the investigator, at immediate risk of death from the event as it occurred (Note: This does not include an							
		had it occurred in a more severe form, might have caused death.); or							
		istent or significant disability/incapacity (substantial disruption of one's ability to conduct normal life functions); or							
	†Results in or prolongs an existing inpatient hospitalization (hospitalization is defined as an inpatient admission, regardless of length of stay, even if the								
	hospitalization is a precautionary measure for continued observation. (Note: Hospitalization [including hospitalization for an elective procedure] for a preexisting								
	condition which has not worsened does not constitute a serious adverse event.); or								
	†Is a congenital anomaly/birth defect (in offspring of subject taking the product regardless of time to diagnosis);or								
	Is a new cancer; (that is not a condition of the study) or								
	Is an overdose (whether accidental or intentional). Any adverse event associated with an overdose is considered a serious adverse event. An overdose that is not								
	associated with an adverse event is considered a non-serious event of clinical interest and must be reported within 24 hours.								
	Other important medical events that may not result in death, not be life threatening, or not require hospitalization may be considered a serious adverse event when,								

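### Table 3's permanent-stop note and its hyperglycemia and hypothyroidism rows give different pembrolizumab instructions for Grade 4 and recurrent Grade 3 events, with no stated order of precedence

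*Combined protocol and SAP*

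**What the plan says.** All the dosing text is in Section 5.2.1.2.1 of the combined protocol and SAP.

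- **Lead-in to Table 3:** "Pembrolizumab must be withheld for drug-related toxicities and severe or life-threatening AEs as per Table 3 below".
- **Type 1 diabetes/hyperglycemia row:** the cell under the restart-timing heading reads "Hold pembrolizumab for new onset Type 1 diabetes mellitus or Grade 3-4 hyperglycemia associated with evidence of beta cell failure". The cell under the discontinuation heading reads "Resume pembrolizumab when patients are clinically and metabolically stable".
- **Hypothyroidism row, Grades 2-4:** both action columns carry the same text, "Therapy with pembrolizumab can be continued while treatment for the thyroid disorder is instituted".
- **Note under the table:** "Note: Permanently discontinue for any severe or Grade 3 drug-related AE that recurs or any life-threatening event".
- **The one marked exception:** the AST/ALT/bilirubin row, at Grades 3-4, reads "Permanently discontinue (see exception below" and points to a footnote. Neither of the two rows above carries such a marker.

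Two other places bear on the reading. Table 6 (Section 7.2.4.1) describes Grade 4 as "Life threatening consequences; urgent intervention indicated". Section 5.9 lists, among the reasons for which a subject must be discontinued, "Unacceptable adverse experiences as described in Section 5.2.1.2", so it takes its meaning from the section that holds Table 3.

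**The concern.** A general rule with no exception sits beneath two specific rows that permit or direct something else. An investigator facing one of the affected events can find support in the same table for stopping the drug for good and for giving it again, and two sites could handle the same event differently while both citing the protocol.

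Two things are at stake. The first is whether a patient is re-exposed to the investigational drug after a life-threatening or recurrent severe event. The second is the tolerability data. Safety and tolerability is a primary objective (Section 3.1), and Section 7.1.1.8 has missed pembrolizumab doses tracked and analyzed as part of it. If the handling of these events depends on which line a site follows, part of the missed-dose count reflects site interpretation and not tolerability.

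**Working it through.** The plan states no figure on this point, so there is none to reproduce. The check is a comparison of the note with the rows, followed by a bound on the number of doses.

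**1. What triggers the note.** It has two limbs: (a) a severe or Grade 3 drug-related event that recurs, and (b) any life-threatening event. Under the Table 6 description, a Grade 4 event meets limb (b).

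**2. The rows that reach Grade 4.** Ten rows of Table 3 do so. Eight end in permanent discontinuation at Grade 4: diarrhea/colitis, AST/ALT/bilirubin (with its footnote), hypophysitis, hyperthyroidism, infusion reaction, pneumonitis, renal failure/nephritis, and all other drug-related toxicity. The two that do not are type 1 diabetes/hyperglycemia and hypothyroidism.

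**3. The note against those two rows.**

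| Event | Note | Row | Conflict? |
|---|---|---|---|
| Grade 4 hyperglycemia with evidence of beta cell failure, or life-threatening new-onset type 1 diabetes | Permanent stop | Hold, then resume when stable | Yes |
| Grade 4 hypothyroidism | Permanent stop | Continuation permitted | Yes |
| Recurrent drug-related Grade 3 hyperglycemia with evidence of beta cell failure | Permanent stop | Hold, then resume; no recurrence limit | Yes |
| Recurrent drug-related Grade 3 hypothyroidism | Permanent stop | Continuation permitted; no recurrence limit | Yes |
| First Grade 3 event of either type, not life-threatening | Not triggered | As above | No |

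**4. Is precedence settled elsewhere?** Section 5.7.1 gives supportive care and refers back to Section 5.2.1 for dose modification. Section 5.9 refers to Section 5.2.1.2. Neither ranks the note against the rows.

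**5. Bound on doses.** Section 5.2, Table 2, plans pembrolizumab on Days -7, 15, 36, 57, 78, 99, 120 and 141, which is 8 doses.

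- Event after the Day -7 dose and before Day 15: 8 - 1 = 7 doses differ at most between the two readings.
- Recurrence after dosing has resumed or continued: at least 2 doses have been given, so 8 - 2 = 6 at most.
- Hyperglycemia: every dose held while waiting for stability is missed under both readings, so the difference shrinks by one for each.
- Whole trial: 57 × 8 = 456 planned doses, so one affected patient moves the missed-dose total by at most 7/456 = 1.5%.

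The documents give no rates for these events, so the expected number of affected patients cannot be computed.

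**The case against.** The best defense is that a specific row overrides a general note. Both rows name the toxicity, name Grade 4 and give an action, and the lead-in tells the investigator to withhold according to the table. This is an ordinary way to read such a table and may be what was meant. It is not stated, however. The note is part of the same table and says "any". The table also shows how it marks an exception, in the liver row, and does not do so here.

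Several narrower points stand and limit the concern.

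- **Grade 4 and life-threatening are not the same term.** The note does not say Grade 4, and Table 6 also has a separate seriousness criterion based on immediate risk of death. On that reading fewer Grade 4 events trigger the note. The conflict remains for those that do, and the recurrence limb is unaffected.
- **The beta-cell condition matters.** A reader might infer that any Grade 4 or second Grade 3 hyperglycemia is re-dosed under the row. The row's text requires evidence of beta cell failure. Drug-related Grade 4 hyperglycemia without it arguably falls under the row for all other toxicity, which agrees with the note.
- **The hypothyroidism row is permissive.** A reader might infer that one patient is ordered both off the drug and back onto it. That does not hold for hypothyroidism: a site that stops the drug breaches nothing in the row. The conflict there is a mandatory stop against a permitted continuation.
- **Table 3 is not the only stopping table.** Table 4 stops the drug for infusion reactions, and Section 11.4 does so for progression. Neither covers the events at issue.
- **The separate guidance on events of clinical interest could not be read here.** Section 5.2.1.2.1 cites it for supportive care, not as a rule on which line of Table 3 governs.
- **Column placement could be an artifact of text extraction.** All the cells of the hyperglycemia row are filled, which makes a lost cell unlikely, but the position should be checked against the source table.

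**Conclusion.** The inconsistency is real and narrow. For Grade 4 or life-threatening events and recurrent drug-related Grade 3 events of two types, Table 3 cannot be followed as written without choosing between its note and its rows, and the documents do not say which prevails. This rests on reading Grade 4 as life-threatening, as Table 6 describes it. If life-threatening is instead judged by the seriousness criterion, the first two conflicts cover fewer patients and the two recurrence conflicts are unchanged.

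The size is at most 7 of 8 doses for an affected patient, fewer after a hold or a recurrence, and an unknown number of patients.

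A reader might infer that a discontinuation-rate endpoint is also at risk, by 1/57 = 1.8 percentage points per patient. The documents do not support that. Section 7.1.1.8 names only missed doses, Section 8.4.2 bases the primary safety analysis on CTCAE toxicities, and no discontinuation-rate endpoint or threshold is defined. The case for acting is the unclear stopping instruction, not an effect on a decision rule. No view is taken here on which clinical rule is right.

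**What to change.** Reconcile the note with the two rows.

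1. State either that the note overrides every row, or which named rows are exempt from it. Say so separately for Grade 4 events and for recurrent drug-related Grade 3 events.
2. Say whether life-threatening in the note means Grade 4 or the Table 6 seriousness criterion.
3. Place the hyperglycemia row's hold, restart and discontinuation text under the matching column headings. As read, the hold criterion sits under restart timing and the resume instruction under discontinuation, which leaves the row with no discontinuation entry.
4. Check that the lead-in to Table 3 and the reference in Section 5.9 still read correctly after the change.

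The sponsor decides which rule applies. The cost is the wording of one note and two table rows in a protocol amendment. Sample size, endpoints and analyses do not change.

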# 5.2.1.2.2 Dose Modification for Cisplatin

Investigators must use cisplatin for this protocol. Substitutions to carboplatin will not be permitted. If toxicities occur, dose reductions as outlined in Tables 3.1 and 3.2 should be performed.

Cisplatin will not be given until the ANC exceeds 1000/mm3 and the platelet count exceeds 75,000/mm3. Myeloid growth factors can be used per local guidelines.

Complete blood count, differential and platelets will be checked weekly during therapy. Cisplatin dose will be reduced for nadir WBC or platelet count as follows:

Nadir			% of 100%
ANC		Platelet	Cisplatin Dose to
			Give
> 1000	And	>75,000	100% (dose level 0)
500 - 999	Or	50-75,000	80% (dose level -1)
< 500	Or	< 50,000	60% (dose level -2)

Table 3.1 - Cisplatin modifications based on Hematology Parameters

Cisplatin will only be given if the serum creatinine is < 1.6 mg/dl. Reduce cisplatin dose for transient rises in creatinine as follows:

 Table 3.2 Cisplatin modifications based on Creatinine Peak

Creatinine Peak	Cisplatin Dose to Give
≤ 1.6	100% (dose level 0)
>1.6-4.0	80% (dose level -1)
> 4.0	60% (dose level -2)

In individuals whose creatinine does not come back down to <1.6 mg/dl, cisplatin should continue to be held.

Neurotoxicity:

Grade 3 hearing loss in the speech frequency range is an indication to discontinue cisplatin. Significant (grade 3) myopathy, weakness, or neuropathy; seizure or paralysis should prompt discontinuation of cisplatin and contact with the principal investigator.

Other adverse events:

Any other grade 4 adverse events, not previously outlined above, will result in decreasing the next weekly dose of cisplatin to 80% (dose level -1). If any grade 4 event persists beyond dose reduction to 60% (dose level -2), cisplatin will be permanently discontinued for the duration of the study.

Dose reductions for grade 3 events, not previously outlined above, will be permitted, but are at the discretion of the individual treating physician. Dose modifications should be performed as: Dose level -1 = 80% dose, Dose level -2 = 60% dose, dose level -3 = hold further cisplatin. Treatment-related grade 3 mucositis, skin toxic effects, xerostomia, dysphagia, and anorexia, are expected toxicities, and dose reduction is not recommended, but will be permitted.

Dose re-escalations are not permitted.

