## 5.2.1.2.3 Dose Modification for Radiation

Reversible radiation mucositis is expected to develop in the majority of patients. This will commonly manifest as Grades I to III in severity. In those rare cases of Grade IV mucositis, radiation can be interrupted for up to5 consecutive radiation treatment days until the reaction subsides to Grade III. However, every effort should be made to keep this treatment break as short as possible. If Grade IV mucositis occurs, systemic chemotherapy should also be held until the reaction subsides to Grade III and then radiation and chemotherapy are resumed.

Toxicities: Common radiation toxicities include mucositis, fatigue, weight loss, regional alopecia, xerostomia, hoarseness, transient ear discomfort, hypogeusia, dysgeusia, dysphagia, and skin erythema and desquamation within the treatment fields. Less common long-term radiation toxicities include hypothyroidism, loss of hearing, chronic swallowing dysfunction requiring permanent feeding tube, and cervical fibrosis. Much less common radiation toxicities include mandibular osteoradionecrosis (<5% incidence with attention to a full dental evaluation as part of pre-treatment planning), and cervical myelopathy (<1% with restriction of spinal cord dose to < 45 Gy).

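### While Grade 4 mucositis is ongoing, Section 5.2.1.2.2 gives cisplatin at a reduced dose and Section 5.2.1.2.3 withholds it; no dose is stated for restarting after the hold

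*Combined protocol and SAP*

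**What the plan says.** **Cisplatin rule (Section 5.2.1.2.2).** After rules for blood counts, creatinine and neurotoxicity, the section adds a residual rule: "Any other grade 4 adverse events, not previously outlined above, will result in decreasing the next weekly dose of cisplatin to 80" per cent (dose level -1). It continues: "If any grade 4 event persists beyond dose reduction to 60% (dose level -2), cisplatin will be permanently discontinued". Mucositis is named in this section only at Grade 3: "Treatment-related grade 3 mucositis, skin toxic effects, xerostomia, dysphagia, and anorexia, are expected toxicities", for which a reduction is allowed but not recommended. The section ends: "Dose re-escalations are not permitted".

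**Radiation rule (Section 5.2.1.2.3).** This section expects mucositis mostly at Grades I to III and describes Grade IV as rare. For Grade IV it says that "systemic chemotherapy should also be held until the reaction subsides to Grade III and then radiation and chemotherapy are resumed". It gives no dose level for the restart.

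**Text that covers both (Section 5.2.1.2).** "The investigator may attribute each toxicity event to the study drug (pembrolizumab), cisplatin, or radiation alone, if appropriate". The same paragraph bases later modifications on the last dose given. It sets no order of precedence between the agent-specific sections, and on this event neither section refers to the other.

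**The concern.** Nothing above the residual rule deals with mucositis, so Grade 4 mucositis comes under it. A site that reads the cisplatin section gives a reduced dose at the next weekly visit. A site that reads the radiation section gives none until the reaction is down to Grade III.

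The trial is multi-site (Section 2.1). Safety is a co-primary endpoint, with particular attention to worsening of known chemoradiotherapy toxicity (Section 4.2.3.1), and adverse event rates are to be compared with historical data (Section 8.4.4). Patients with the same severe toxicity could be dosed differently according to which page the site consulted, and the tolerability data would mix two dosing rules.

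**Working it through.** The plan gives no figure to reproduce here. The check sets the two rules side by side and then counts cisplatin under each for the same clinical course.

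**Inputs**
- Planned cisplatin: 40 mg/m2 on days 1, 8, 15, 22, 29 and 36 (Section 5.2, Table 2; Section 5.2.1.3.2). Total 6 × 40 = 240 mg/m2.
- Reduced doses: 80% is 0.8 × 40 = 32; 60% is 0.6 × 40 = 24 (Section 5.2.1.2.2).
- A dose delayed beyond its window (±2 days) is not given, and treatment resumes on the next scheduled day (Section 6, note 2). A week's hold therefore counts as 0.

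**Assumptions for the illustration**
- Full doses are given before onset.
- If Grade 4 persists, the step from 80% to 60% comes at the next weekly dose, and cisplatin stops at the dose after that. Section 5.2.1.2.2 does not time these steps.
- After a hold, the restart is shown at full dose and, in brackets, at 80%, because Section 5.2.1.2.3 states neither.

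**Totals in mg/m2, clinical course held fixed**

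| Course | 5.2.1.2.2 | 5.2.1.2.3 | Difference |
|---|---|---|---|
| Onset before day 29, persists | 160+32+24 = 216 | 160+0+0 = 160 | 56 |
| Onset before day 29, subsides after one week | 160+32+32 = 224 | 160+0+40 = 200 (160+0+32 = 192) | 24 (32) |
| Onset before day 22, persists | 120+32+24+0 = 176 | 120+0+0+0 = 120 | 56 |
| Onset before day 22, subsides after one week | 120+32+32+32 = 216 | 120+0+40+40 = 200 (120+0+32+32 = 184) | 16 (32) |

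As a share of the planned total, the largest difference is 56/240 = 23% and the smallest is 16/240 = 7%.

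**Event already at Grade III before the next dose.** With onset after day 22 and resolution to Grade III before day 29, no dose is missed under either section. Section 5.2.1.2.2 gives 160+32+32 = 224. Section 5.2.1.2.3 gives 160+40+40 = 240 at full dose, or 224 at 80%. The sections agree if the restart is at 80% and differ by 16 if it is at full dose. In that course the only open point is the restart dose.

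**The case against.** **The two rules can be combined.** The residual rule sets a dose level and the mucositis rule sets timing, so a site could hold until Grade III and then give 80%. Section 5.2.1.2.2 itself pairs a hold with a reduction for counts and creatinine. This reading is available once the event has subsided, and to that extent the objection stands. It does not cover an ongoing event. For counts and creatinine the section states the hold; its Grade 4 sentence states none. The sequence of 80%, 60% and then stopping also makes sense only if cisplatin is given while Grade 4 continues.

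**The specific rule should override the general one, or attribution decides.** No precedence is stated. Attribution to one agent is optional, and Section 5.2.1.2.3 acts on chemotherapy even though it concerns radiation mucositis. Letting it govern would still leave the restart dose open: basing the dose on the last one given could mean full dose after a first event.

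**The event is rare.** This stands. The protocol expects mucositis in most patients, but only Grade 4 triggers the conflict.

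**Stronger readings that the documents do not support**
- A reader might infer that one patient could receive anywhere from 160 to 224 mg/m2, or from 120 to 216 with earlier onset. Those ranges pair a course that subsides with one that persists. With the course fixed, the differences are those in the table.
- A reader might infer that Section 5.2.1.2.3 contradicts itself because the break is limited to 5 "consecutive radiation treatment days until the reaction subsides to Grade III", so that a patient still at Grade IV on the sixth day must both restart and wait. The wording is permissive. Section 5.2.2.9 treats 5 days as an ideal limit and classifies prolongation of 6-10 and of more than 10 days. Section 7.1.1.8 requires consultation with the principal investigator for interruptions over one week.
- A reader might infer an effect on the complete response rate. Nothing in the documents allows that to be estimated.

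**Conclusion.** The conflict is real and limited. While Grade 4 mucositis is ongoing, one section gives a reduced cisplatin dose and the other withholds it, and nothing in the protocol says which prevails. Once the event has subsided to Grade III, what remains is the unstated restart dose.

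With the clinical course fixed, the difference is 56 mg/m2 of a planned 240 if Grade 4 persists, and 16 to 32 if it subsides after one week. These figures illustrate and do not predict. They rest on the assumed onset times and on the step to 60% coming at the next weekly dose; a later step would raise the total under Section 5.2.1.2.2 and widen the gap.

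No sample size, power, alpha or analysis rule is affected. The point matters for consistent handling of a severe toxicity across sites and for reading the tolerability data. It should be corrected, but it does not threaten the design.

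**What to change.** Reconcile Sections 5.2.1.2.2 and 5.2.1.2.3 in the next amendment by stating:
- whether Grade 4 mucositis is covered by the residual Grade 4 rule or excepted from it;
- which section governs cisplatin for this event, including while Grade 4 persists;
- the dose level at which cisplatin restarts after a hold;
- a cross-reference in each section to the other.

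Which rule to adopt is the sponsor's clinical decision. The cost is two or three sentences in an amendment and a memo to sites, with no change to the sample size or the analyses.
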